166 participants will be recruited from an outpatient cardiac rehabilitation center in China. Eligible participants will be randomly assigned into one of two groups. (1) Intervention group (IG): simultaneously physical activity (PA) and fruit and vegetable intake (FVI) (week 1-8); and (2) the waiting list control group (WCG): not participate in any support program during the intervention period. The testing indicators consist of PA (International Physical Activity Questionnaires; IPAQ), self-reported FVI, combined healthy lifestyle, social-cognitive variables of two behaviors (self-efficacy, intention, planning, social support), quality of life and depression. All indicators will be conducted at the beginning of intervention (T1), at the end of intervention (T2), and three-month follow-up (T3). All data collection will be completed via e-health learning website with electronic questionnaires.

The current study will examine whether the cardiac rehabilitation patients in IG increase their PA level and FVI, improve the social-cognitive variables of PA and FVI, and enhance mental health outcomes in comparison with control condition; and whether the social-cognitive variables mediate the association between intervention and adopting a healthy lifestyle. We believe the study findings will contribute to the current multiple health behaviour intervention research and support Chinese cardiac patients to maintain rehabilitation outcomes and cultivate a healthy lifestyle.

4. The project aims, its long-term significance:

(State the aims, identify the key issues and problems being addressed and list the possible outcomes of the research project, as well as its significance and value) (Maximum 600 words or 1 page)

Key issues and problems:

Medical rehabilitation after severe health issues (e.g., cardiovascular diseases such as stroke or orthopedic issues such as a knee replacement) is a crucial component of the recovery process. Patients are physically trained under guidance and prepared for their return to everyday life at rehabilitation discharge. Regular physical activity and healthy dietary plays an irreplaceable role in this process to get the patients to adopt a healthy lifestyle and maintain their treatment success with the aim of becoming resilient and being able to return to work (Russell & Bray, 2009; Xie et al., 2016;). However, the significant contribution of rehabilitation depends mainly on its successful implementation in daily life after the formal rehabilitation process. Literature reviews show that it is often difficult for patients to integrate the learning outcomes from rehabilitation into their daily life (e.g., Li & Shao, 2017). Especially in China, because of the limitation of rehabilitation aftercare, many family-based health care offers are inaccessible to patients, especially those who live in decentralized residential areas, which subsequently aggravate the difficulties for cardiac patients to maintain the treatment success and transfer the learning outcomes of clinical rehabilitation. Therefore, the present study suggests that aftercare which the patients can follow at home (e.g., website plus SMS and Wechat prompts) should be offered (Kordy, Theis, & Wolf, 2011; Yan, Yang, & Nong, 2017).

This study aims to examine the efficacy of an 8-week e-health intervention on physical activity (PA) and fruit and vegetable intake (FVI) in Chinese cardiac patients. In addition, this study will detect why the intervention is effective and to identify the social-cognitive variables that may account for adopting a healthy lifestyle.

The possible outcomes of the research project are to provide knowledge on:

1. Participants in the intervention group (IG) increase their PA levels and FVI portion in comparison with a control group.
2. Participants in the intervention group (IG) improve their social-cognitive variables of PA and FVI in comparison with a control group.
3. Participants in the intervention group (IG) enhance their mental health outcomes in terms of quality of life and depression level in comparison with a control group.
4. The social-cognitive variables of PA and FVI mediate the association between intervention and adopting a healthy lifestyle.

Long-term significance:

This study will make a significant contribution with new insights toward the current multiple

health behaviour intervention in rehabilitation aftercare in China. By using innovative theory-based e-health learning technology, the tailored intervention program can help cardiac patients form healthy lifestyle habit in daily life.

In addition, this study will apply the Health Action Process Approach (HAPA; Schwarzer, 2008) model, which has been proved to be applicable to diverse participants in different health behaviour, so that contribution can be made to the development of the HAPA model in health behaviour research among Chinese cardiac patients.

To our knowledge, very few studies have provided evidence for detecting the psychological mechanism of multiple health behaviours change among Chinese population. This study will explore whether the social-cognitive variables of PA and FVI can be mediators of intervention and adopting a healthy lifestyle.

5. Objectives (State the objectives in point form):

- Objective 1:** To examine the efficacy of an e-health intervention on single behaviour indicator (PA and FVI) and adoption of a healthy lifestyle (the synthesis of both behaviours) in comparison with a control group.
- Objective 2:** To examine the efficacy of an e-health intervention on social-cognitive variables of PA and FVI (self-efficacy, intention, action and coping planning, social support) in comparison with a control group.
- Objective 3:** To examine the efficacy of an e-health intervention on mental health outcomes, including perceived quality of life, and depression level in comparison with a control group.
- Objective 4:** To examine whether there are mediation effects of social-cognitive variables of PA and FVI on adopting a healthy lifestyle.

6. Background of research, research plan and methodology: : (Maximum 6 pages, excluding references)

[Summary of related work that has already been done and an outline of previous and alternative approaches to the problem -

(a) By others (give key references)

(b) By the investigator(s) (give key references)

(c) Progress report (for on-going projects)]

[Explain, in terms of the educated layman, the novel idea which you will be introducing to tackle the problem in question. Please include key references. Attach a draft questionnaire should the research plan involve a survey/interview.]

Background of research

(a) Work done by others

This study will apply the Health Action Process Approach (HAPA; Schwarzer, 2008) as the theoretical backdrop, which suggests there are two distinctive phases during the health behaviour change process. First is the motivation phase, which plays an important role before a goal is set. Subsequently individuals enter the volitional phases. This distinction allows the tailored intervention to the variables which correspond to a specific process. In particular, the motivation must occur before individuals change their unhealthy habits. Therefore, individuals may benefit most from interventions that will increase risk perception, self-efficacy, and the positive outcome expectancies (Schwarzer, Cao, & [name], 2010). The purpose is to lead towards a specific intention (e.g., "I intend to eat some fruit and vegetables today") and once they forming the intention, individuals enter into volition processes. People benefit the most from planning interventions, which can be the bridge from intention to behaviour (Reinwand et al., 2016). At this process, individuals will learn to make specific plans (e.g., when, where and how to eat fruit and vegetables), determine priorities, and to translate their action plans into behaviour. Self-regulatory skills are necessary to maintain their progress once people start to initiate a healthy behaviour. Positive behaviour change will be guided by self-efficacy, as this regulates how much effort is invested in goal achievement and how much persistence is maintained if obstacles and setbacks occur. Additionally, promoting perceived social support from people's social context is equally important in preventing relapse (Schwarzer, 2008; Figure 1).

Considerable evidence has proved the effectiveness of interventions based on the HAPA model in improving PA (Schwarzer, [name], & Ziegelmann, 2008), healthy diets (Wiedemann et al., 2008), and other health behaviours (e.g., Payaprom, Bennett, Alabaster, & Tantipong, 2011).

[figure not shown]

Figure 1: The Health Action Process Approach (HAPA; Schwarzer, 2008)

During the past two decades, multiple health behaviour interventions have become more plausible. Previous studies indicate that interventions implementing on both PA and healthy diet behaviour can be effective for cardiac patients (Liang, Duan et al., 2017; Storm et al., 2016). However, one major question needs to be tackled with is how best to achieve multiple health behaviour change, including whether to intervene sequentially or simultaneously. Many studies have conducted sequential approach on PA and dietary behaviour and found mixed outcomes (Duan et al., 2017; Fleig et al., 2014; Storm et al., 2016). On the contrary, one view points out that PA and dietary

behavior are all health-enhancing behaviours and they are closely correlated. As such there might be additive or synergistic when intervening simultaneously (Atkins & Clancy, 2004). Meanwhile, the simultaneous approach is suggested to be time and cost-effective (Prochaska et al., 2010). Some studies have found support for the simultaneous approach (e.g., Kypri & McAnally, 2005). However, there is still limited evidence regarding the efficacy of an intervention with simultaneous approach to improve PA and healthy dietary behaviour in Chinese cardiac patients.

In addition, employing the internet technology to deliver intervention of multiple health behaviour promotion has a number of advantages (Webb et al., 2010). In particular, the internet intervention can (a) be delivered to large numbers of people at a low cost, (b) ensure that the intervention is accessible at any time and any location, and (c) provide follow-ups and feedback with personalized methods. Furthermore, the use of internet technology has become increasingly prevalent in rehabilitation aftercare (Reinwand et al., 2016; Widmer et al., 2014). A meta-analysis by Webb et al. (2010) indicated that online interventions targeting multiple behaviours had a small but significant effect size ($d = 0.12$, $k = 10$, 95% CI 0.08 to 0.17) on behaviours. Meanwhile, this study also pointed out that additional short message service (SMS) periodic prompts may improve the efficacy of e-health interventions (Webb et al., 2010). Moreover, as a prevalent social media for the Chinese population, the *Wechat* has been also applied in the rehabilitation of patients with lumbar disc herniation (Gao et al., 2017).

(b) Work done by the investigators

On the basis of the HAPA model, a series of e-health intervention have been conducted by the investigators. As a Co-I, [name] et al. developed an 8-week web-based intervention on PA and fruit and vegetable intake (FVI) towards population with lower cardiovascular risk in German and Dutch (Reinwand, Kuhlmann, Wienert, de Vries & [name], 2013). The intervention effects have been well supported (Storm et al., 2016; Reinwand et al., 2016).

The principal investigator (PI) of this project has been collaborating with [name] to design tailored 8-week e-health intervention programmes in Chinese samples since 2014. With the support of university grants, the PI has completed some pilot work on this intervention program in Chinese university students and Chinese cardiac rehabilitation outpatients. In particular, 1) to design the tailored Chinese intervention materials (e.g., information about the benefits of PA and FVI, prompts to promote explicit goal setting, and feedback provided on participants' performance); 2) to validate the intervention materials with regard to the understanding in Chinese samples; 3) to build an 8-week explicit intervention website module (sequentially PA in week 1-4, and FVI in week 5-8); 4) to refine and optimize the website functions by implementing online tests with a small sample size. Based on the preparation work above, the PI conducted two e-health intervention studies. Regarding the university students, the intervention effects on PA and FVI are supportive (Duan et al., 2017). In terms of the cardiac rehabilitation patients, manuscript writing is in progress (Duan et al., under preparation). Results of this study indicated that time by group interaction effects were significant both in PA ($\eta^2 = .14$, $p < .01$) and FVI ($\eta^2 = .43$, $p < .001$). Moreover, all psychosocial variables for PA and FVI showed superior intervention effects with an effect size of η^2 ranging from .09 to .23. With the help of e-health learning program, patients were about 1.7 times more likely to practice or maintain a healthy lifestyle in comparison with patients in a control condition (OR = 1.68, 95% CI = 1.94-2.35, $p < .01$). Findings in this pilot study indicate the overall effects of a web-based PA and FVI intervention in Chinese cardiac patients. In addition,

measurement tools and web-based intervention materials used in this pilot study provide the foundation for further intervention study.

However, based on the previous literature review, there is still limited evidence regarding the web-based intervention with simultaneous approach to improve PA and healthy dietary behavior in Chinese cardiac patients (Wu & Li, 2017). In addition, the psychological mechanism of health behavior change has not been addressed in the previous study among Chinese cardiac patients (Duan et al., 2017). Thus, this study attempts to fill the research gap and provide empirical evidence for these aforementioned issues.

Methodology

Participants:

All rehabilitation participants (≥ 18 years) who have no contraindication with respect to PA or FVI will be eligible to participate in the study. In particular, participants must meet the inclusion criteria of (1) no restriction of physical mobility under the cardiac function at entry; and (2) no restriction of relevant disease such as diabetes or fruit allergies. As the study involves an online website and mobile phone SMS, only participants with access to the Internet via mobile phone will be enrolled.

Patients will be recruited from one outpatient cardiac rehabilitation centre in Guangdong General Hospital, Guangzhou, China. For the main study, the sample size will be estimated by using G*Power 3.1 software with MANOVA of repeated measures approach. For achieving medium effect size of 0.25 (Duan et al., 2017), with a power ($1-\beta$) of 0.8 and alpha of 0.05, the total sample size will be 116. Assuming a dropout rate of approximately 30%, a total of 166 participants will be required for the study evaluation.

Procedure:

(1) Validation stage. There are 4 steps need to be implemented before conducting main study. Step 1: based on the established intervention materials with sequential intervention mode in previous study (Duan et al., 2017), investigators will work out a new intervention protocol corresponding to simultaneous intervention mode (PA + FVI in week 1-8); Step 2: to refine and adjust the language of intervention materials based on the feedback of patients participating in the previous study to make the information more understandable and acceptable; Step 3: to develop two website modules for intervention group and wait list control group; Step 4: to evaluate website module functions by conducting online tests with a small sample size.

(2) Main study stage. Participants who will receive outpatient rehabilitation will be informed about the purpose of study by their physicians with relevant information materials. Upon patients show their interest and consent, they will sign study consent inform and be invited to finish the online registration within one week (T0). Afterwards, patients will be randomly assigned into one of two groups. (1) Intervention group (IG): simultaneously, both PA and FVI for 8 week; and (2) the waiting control group (WCG): patients will not receive any support programme during the intervention period but will be provided with the same intervention at follow-up six-month after the intervention.

The data will be collected at the beginning of intervention (T1), at the end of intervention (T2), and at 3-month follow-up (T3). All website hyperlinks for the questionnaire surveys at T1, T2, and T3 as well as for the weekly e-health learning program will be delivered by the researchers to the patients via Wechat platform (a Chinese social media app with multi-functions).

Intervention:

The 8-week e-health intervention will target HAPA-based social-cognitive variables of

PA and FVI. Particularly, Week 1: risk perception and outcome expectancies; Week 2: goal setting; Week 3: development of action plans; Week 4: revision and adjustment of previous action plans; Week 5: development of coping plans; Week 6: revision and adjustment of previous coping plans; Week 7: development of perceived social support; Week 8: revision and adjustment of previous social support. Self-efficacy will be a fixed intervention variable involved from week 2 to week 8. Table 1 indicates intervention variables, intervention goals and intervention content.

Table 1: Variables, goals and content of intervention across 8 weeks

Intervention Variables	Physical Activity + Fruit and Vegetable Intake							
	week 1	week 2	week 3	week 4	week 5	week 6	week 7	week 8
Risk perception	✓							
Outcome expectancies	✓							
Self-efficacy		✓	✓	✓	✓	✓	✓	✓
Goal setting		✓						
Action plans			✓	✓				
Coping plans					✓	✓		
Social support							✓	✓
Intervention goals	1. improving the risk awareness of inactive lifestyle and unhealthy diet 2. stimulating positive outcome expectancies and motivating intention formation	1. enhancing motivational self-efficacy for PA and FVI 2. setting a general goal of health behavior and forming the intention of PA and FVI	1. setting action plans for PA and FVI 2. boosting motivational self-efficacy for PA and FVI	1. further confirming appropriate action plans for PA and FVI 2. further enhancing motivational self-efficacy for PA and FVI	1. setting coping plans for PA and FVI 2. enhancing self-efficacy on maintaining PA and FVI	1. further confirming appropriate coping plans for PA and FVI 2. further enhancing self-efficacy on maintenance of PA and FVI	1. promoting perceived social support on PA and FVI 2. enhancing recovery self-efficacy to prevent unhealthy behaviour relapse	1. further promoting perceived social support on PA and FVI 2. further enhancing recovery self-efficacy to prevent unhealthy behaviour relapse
Intervention Content	informing the risk of inactive behaviour and unhealthy diet introducing and promoting the benefits of physical activity (PA) and fruit and vegetable intake (FVI).	assessing motivational self-efficacy; encouraging patient to build confidence in PA and FVI setting goals for PA and FVI, as well as general health goal	learning how to make specific action plans for PA and FVI taking examples of successful case about action plan implementation	reviewing the implementation of action plans; adjusting action plans taking examples of successful case about action plan implementation and adjustment	finding difficulties of plan implementation, making coping plan taking examples of successful case about health behaviour adherence	reviewing the implementation of coping plans; adjusting coping plan Take examples of successful case about health behaviour adherence	reviewing perceived social report on PA and FVI taking examples of successful case about behaviour relapse prevention	further reviewing perceived social report taking examples of successful case about behaviour relapse prevention

Additionally, some behaviour change techniques will be employed in the intervention in order to facilitate the implementation and maintenance of behaviour. For example, two types of feedback will be provided. Participants will receive individualized feedback on their behaviour performance 4 weeks ago, 3 weeks ago, 2 weeks ago and 1 week ago respectively. In addition, normative feedback on the criterion-based behaviour recommendation will be presented as well (e.g., accumulated at least 150 minutes with moderate intensity of PA per week, 5 portions of FVC per day) (see example in Figure 2). Moreover, examples of role models will be provided throughout the intervention to support participants to set goals and develop plans.

In addition to the intervention on web-site, SMS reminder will be sent to participants weekly prior to each intervention program in order to remind patients to attend the weekly intervention (e.g., "Dear patients, the coming learning session will start tomorrow. We kindly remind you to participate in it by clicking the hyperlink showed on the Wechat tomorrow. Have a nice day! "). Sequentially, Wechat message will be sent to participants on the next day for accessing the intervention website (e.g., "Here is the intervention hyperlink for Week two. Please click on it. www.ehealthlearningchina.com/patient/two_b.php").

[figure not shown]

Figure 2: Individualized and normative feedbacks regarding the portion of fruit and vegetable intake in average per day

Measures:

The standardized electronic questionnaires have been validated in the previous pilot study with Chinese cardiac patients (Liang, Duan et al., 2017), which consists of the following four parts.

1. Behaviour indicators

Physical activity (PA): The level of PA will be measured through the short Chinese version of the IPAQ questionnaire (Macfarlane et al., 2007). Participants will be asked to estimate the number of days and hours spent for vigorous, moderate and walking activities during the past week. **Fruit and vegetable intake (FVI):** FVI will be measured with four items, including fruit or vegetable juice, fruit, cooked or steamed vegetables, and raw vegetables (Rafferty et al., 2002). Respondents will be asked to count the number of portions of fruit and vegetables they consumed on average during a typical day. **Combined healthy lifestyle indicator:** In order to combine two behaviours, PA and FVI will be categorized according to whether or not the participants meet the health recommendations ([name], Fleig, Wiedemann, & Schwarzer, 2015). Based on the health guidelines for cardiac patients, the thresholds of 150 minutes PA per week (WHO, 2010) and 5 portions of fruit and vegetables (WHO, 2004) will be chosen. We use 1 and 0 to denote whether participants meet both recommendations or not.

2. Social-cognitive indicators of PA and FVI

Self-efficacy: Self-efficacy will be assessed with three dimensions consisting of motivational, maintenance and recovery self-efficacies with the stem "I am certain that..." followed by 5 items for PA such as "...I can be physically active permanently at a minimum of 5 days a week for 30 minutes even if it is difficult", or followed by 5 items for FVI such as "...I can eat 5 portions of fruit and vegetable a day even if it is difficult." (Cronbach's α for PA= .88; Cronbach's α for FVI= .92) (Luszczynska & Sutton, 2006). **Intention:** Intention for PA will be assessed with the stem "I intent to do for at least 30 minutes as day on minimum 5 days a week or at least 150 minutes a week with..." followed by 3 items such as "... vigorous sport", "...moderate PA" and "...mild PA". Intention for FVI will be measured by the stem "I seriously intend to..." followed by 3 items such as "eat at least 5 servings of fruit and vegetable each day"

and "... drink each day at least one glass of fruit or vegetable juice" (Cronbach's α for PA= 0.34; Cronbach's α for FVI= 0.73) ([name] et al., 2009). **Planning:** Planning indicator will be assessed with 6 items, consisting of action planning and coping planning with 3 items for each dimension. The item of action planning for PA will be asked such as "...which concreted PA I will pursue", for FVI such as "...how I will prepare the food" (Cronbach's α for PA= 0.86; Cronbach's α for FVI= 0.91). The items of coping planning for PA will be asked such as "...how I can stay active, even if something happened", for FVI such as "what I can do in difficult situations, in order to remain true to my own resolutions" (Cronbach's α for PA= 0.87; Cronbach's α for FVI= 0.93) (Schwarzer, 2008). **Social support:** This scale will be measured with the stem as "How do you perceived your environment?" followed by 3 items for PA such as "...People like my friends help me to stay physically active", or followed by 3 items for FVI such as "...People like my friends help me to eat healthily" (Cronbach's α for PA= 0.72; Cronbach's α for FVI= 0.69) (Jackson, [name] & Gray, 2011).

3. Variables related to mental health status

Perceived Quality of life: This indicator will be assessed by using the short version of WHO Quality of Life-BREF (WHO, 1993). Respondents will be firstly asked about their general quality of life as "How would you rate your quality of life?", then 7 items in physical health subdomain will be used, such as the example item "To what extent do you feel that physical pain prevents you from doing what you need to do?" (Cronbach's α = 0.89). **Depression:** Level of depression will be measured with the use of the Center for Epidemiologic Studies Short Depression Scale (CES-D 10) (Andersen et al., 1994). Respondents will be asked with the stem as "In the past week how often I feel ..." followed by 10 items such as "...I was bothered by things that usually don't bother me" (Cronbach's α = 0.74).

4. Sociodemographic information

Gender, age, marital status, education level, rehabilitation treatment history, current work status, self-reported height and weight.

Statistical analysis:

All data will be analyzed by using SPSS 23.0 software. Independent samples t-tests and Chi²-tests will be adopted to examine the characteristics of drop out and compare the differences of baseline data at T1. Statistical significance will be set at 5% level (two-tailed).

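### By the stated order, the only baseline (T1) is self-reported after randomisation, and nothing in the plan withholds allocation until T1 is submitted

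*Combined protocol and SAP*

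**What the plan says.** In the combined protocol and SAP, Methodology, Procedure (2) Main study stage, patients consent and will "be invited to finish the online registration within one week (T0). Afterwards, patients will be randomly assigned into one of two groups". The same section continues: "The data will be collected at the beginning of intervention (T1), at the end of intervention (T2), and at 3-month follow-up (T3"). The project abstract agrees: "All indicators will be conducted at the beginning of intervention (T1), at the end of intervention (T2), and three-month follow-up (T3"). T0 is described only as registration, and no outcome is assigned to it.

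The Statistical analysis section treats T1 as the baseline; its t-tests and chi-squared tests will "compare the differences of baseline data at T1". The repeated-measures MANOVA takes T1, T2 and T3 as the levels of time.

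On delivery, the Procedure section has the researchers send "All website hyperlinks for the questionnaire surveys at T1, T2, and T3 as well as for the weekly e-health learning program" over one Wechat channel. The Intervention section adds: "SMS reminder will be sent to participants weekly prior to each intervention program in order to remind patients to attend the weekly intervention". The validation stage (Step 3) provides a separate website module for each arm. The control arm receives no support programme during the intervention period.

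**The concern.** Every outcome is a self-report on an electronic questionnaire, and the comparator is a waiting list. A patient who knows the assignment when answering T1 may answer differently for that reason.

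The most exposed items are the intention items, which ask about the near future, and the planning items, which ask about the coming month, although these are worded as planning already done. They matter because Objective 2 is "To examine the efficacy of an e-health intervention on social-cognitive variables of PA and FVI" and Objective 4 uses the same variables as mediators. Items that recall past activity, intake, mood or quality of life are less exposed.

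A shift at T1 enters the time-by-group contrast directly. The planned comparison of the arms at T1 cannot tell it from chance imbalance.

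Separately, a patient who is randomised but never submits T1 has no observed baseline. Missing data are to be imputed by EM within each measurement time. Read literally, that leaves such a patient no T1 answers to impute from. The number of such patients is not stated, and no size is claimed for this part.

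**Working it through.** **Order of events.**

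| Step | Event | Source |
|---|---|---|
| 1 | Information and consent | Procedure (2) |
| 2 | Online registration, T0 | Procedure (2) |
| 3 | Random assignment | Procedure (2) |
| 4 | T1, at the beginning of the intervention | Procedure (2); abstract |
| 5 | T2, T3 | Procedure (2); abstract |

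That step 4 follows step 3 is read from the order of the text and the definition of T1; no sentence says so outright. No available section places an outcome before step 3, says when patients learn their arm, or makes the arm-specific module depend on T1 having been submitted.

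**Numbers per arm.** The Participants section says "the total sample size will be 116" before dropout. With 30% dropout, 116/(1 - 0.30) = 165.7, rounded up to the plan's 166. Assuming equal arms, this is 116/2 = 58 to 166/2 = 83 per arm. The 116 itself cannot be reproduced without the G*Power option and the correlation, which are not given. That does not affect this point.

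**Illustration: assumptions.** One outcome of the exposed type, unit SD, the same correlation rho (0.3, 0.5 or 0.7) between any two of the three times, two-sided alpha 0.05. Let s be the shift at T1 (intervention minus control), p the share of it that persists to T2 and T3, and d the true effect at T2 and T3. None of s, p, rho and d comes from the documents.

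**Formula.** The group differences at T1, T2 and T3 are (s, d + ps, d + ps). Both changes from T1 therefore differ between arms by delta = d - (1 - p)s. Hotelling's test of the time-by-group contrast has noncentrality

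lambda = (n/2)(2/3) delta²/(1 - rho) = n delta²/[3(1 - rho)],

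referred to F with 2 and 2n - 3 degrees of freedom. If p = 1 the shift cancels.

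**Worked case, n = 58, rho = 0.5, s = 0.1.**
- Null, none persists: delta = -0.1, lambda = 58 × 0.01/1.5 = 0.387, rejection 7.9%.
- Null, half persists: delta = -0.05, lambda = 58 × 0.0025/1.5 = 0.097, rejection 5.7%.
- Effect giving 80% power: d = 0.506, lambda = 9.90.
- Same effect, none persists: delta = 0.406, lambda = 6.37, power 59.9%.
- Same effect, half persists: delta = 0.456, lambda = 8.04, power 70.7%.

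**Null rejection (%), range over n = 58 and 83 and rho = 0.3 to 0.7.**

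| Shift s (SD) | All persists | Half persists | None persists |
|---|---|---|---|
| 0.05 | 5.0 | 5.1-5.4 | 5.5-6.7 |
| 0.1 | 5.0 | 5.5-6.7 | 7.1-12.4 |
| 0.2 | 5.0 | 7.1-12.4 | 14-38 |

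**Power (%) at 58 per arm, shift of 0.1 SD.** The true effect is set to give 80% without a shift: d = 0.60, 0.51, 0.39 SD for rho = 0.3, 0.5, 0.7.

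| Direction | All persists | Half persists | None persists |
|---|---|---|---|
| Rise in the intervention arm | 80 | 72.3 / 70.7 / 67.7 | 63.4 / 59.9 / 53.2 |
| Opposite shift | 80 | 86.3 / 87.3 / 89.0 | 91.1 / 92.5 / 94.7 |

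With the same effects and all 83 per arm retained, power is 92.6% without a shift. A 0.1 SD rise lowers it to 84-87% (half persists) or 70-80% (none).

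**The case against.** The strongest reply is that the harmful step is not in the documents. Randomising before baseline does no damage through expectation if patients do not yet know their arm, and nothing says they are told before T1. The text is a page-limited grant proposal, and the consent pages, where disclosure might be described, were not available. This stands, and it limits the point to an unaddressed risk.

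A reader might infer from the reminders that intervention patients learn their arm before answering T1. The documents do not support that. The only example link is for Week two, no Week 1 message is shown, and a shared channel says nothing about order. What holds is that the plan does not place the Week 1 reminder or link after T1.

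The size rests wholly on assumed shifts, so the tables span several and cannot show that the problem is large. A reader might also carry the power loss to below 50% by shrinking the true effect until 83 per arm again gives 80%. The plan sets 80% power at 116 in total and adds patients only for dropout, so the floor for a 0.1 SD shift is 53%.

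The pilot, in the section on the investigators' own work, reports eta-squared of .09 to .23 for the psychosocial variables. If these are read as multivariate effects (an assumption), then with 58 per arm, a 0.1 SD rise and no persistence, power falls from 86% to 62-72% at .09 but stays above 99% at .23. The loss may therefore be small.

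Finally, missing data are not ignored: dropout characteristics are tested and EM imputation is planned. Neither restores a baseline that was never observed.

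**Conclusion.** The point holds as an avoidable design risk. By the stated order, the sole baseline is taken after assignment, by self-report, in a trial whose control arm knowingly waits, and no available text protects it. Bias is not shown, and a reader should not infer that it is present or that it favours the intervention: a T1 rise in the intervention arm hides benefit, the opposite shift exaggerates it, and a shift that persists fully cancels.

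The documents give no size. Under the assumed shifts of 0.05 to 0.2 SD, null rejection runs from close to nominal (5.1%) to 38%, depending on the shift, its persistence, the correlation and the number per arm. The upper end needs a 0.2 SD shift that vanishes entirely by T2, with 83 per arm and a correlation of 0.7.

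The change should be made because it is cheap and improves on the stated order. Confidence is medium, since knowledge of the arm at T1 is inferred as possible, not documented.

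**What to change.** Have patients submit the full T1 questionnaire online immediately before randomisation. Then randomise, send the group-specific link and begin Week 1 promptly. State in the plan that T1 is a pre-randomisation baseline, so that every randomised patient has an observed T1.

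The cost is some wording and a change in the order of two website steps, since all questionnaires are already electronic. There are two downsides. A gap opens between T1 and Week 1; the documents do not give its length, and it should be kept short because the activity and intake items look back over only the past week. Patients who do not complete T1 are not randomised.

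The minimum alternative is to keep the order but state that allocation, the Week 1 reminder and the Week 1 link are withheld until T1 is submitted, and to report T1 completion by arm. This deals with the expectation shift but not with patients lost between assignment and T1.
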